The dosing of miglustat in the Maegawa study was described as follows: "In order to achieve adequate levels of miglustat in the central nervous system, the highest doses already examined in LSDs [lysosomal storage diseases] were chosen. The drug was administered at a maximum dose of 600 mg/day, divided into three doses. As the study was performed in a pediatric population, the dose was adjusted to the body surface area (BSA) of each patient." Children with BSA < 0.8 m² received miglustat dosed at 50 mg-90 mg 3 times daily, titrated to the maximum tolerated dose (up to 270 mg per day). The major dose-limiting drug-related adverse events that resulted in dose reductions of miglustat in Maegawa's study were gastrointestinal side effects secondary to miglustat's inhibition of disaccharidases in the gut, resulting in intolerance of dietary carbohydrates. For patients with BSA < 0.8 m², final doses, after titrating to maximum tolerated dose, ranged widely from 360 mg/m² to 450 mg/m², and the milligrams administered per day ranged from 15 mg/kg/day to 20.9 mg/kg/day.

Subjects with BSA 0.8 – 1.3 m² will receive the goal dose of 100 mg miglustat three times daily, or the maximum dose tolerated up to 100 mg miglustat three times daily.

Rationale: In Maegawa's 2009 study, patients with BSA within 0.8 m² to 1.3 m² received 100 mg 3 times daily.

Subjects with BSA > 1.3 m² will receive the maximum dose tolerated, up to 200 mg miglustat three times daily.

Rationale: In Maegawa's 2009 study, patients with BSA > 1.3 m² received 600 mg per day (200 mg 3 times daily), or the maximum tolerated dose, up to 200 mg 3 times daily.

10.11 Use of miglustat in this study. Before starting miglustat, patients will be initiated on the ketogenic diet, with goal of achieving a 4:1 ratio, and showing stability on the ketogenic diet for 2 weeks before starting miglustat therapy.

Miglustat dose will be prepared by dissolving contents of one 100 mg capsule in 10 ml of water. Only one dose of miglustat will be prepared at a time and the preparation must be used immediately and not stored for future use. Any unused solution during the initial dose escalation should be discarded. Miglustat dose will be prepared by patient's caregiver and caregiver will be counseled on pregnancy category C status and sperm parameter studies of miglustat. Caregiver should use a mask and gloves during preparation of miglustat solution.

The following written instructions will be given to the parents:

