11.4 Initiation and management of the ketogenic diet. The ketogenic diet must be initiated and managed by a clinical ketogenic diet team. Members of this team will include a ketogenic dietician and neurologist trained in the ketogenic diet. The ketogenic diet team will work in collaboration with the patients' doctor [name], PhD, Pediatric Geneticist and Primary Care Pediatrician; and [name], Clinical PharmD. The patients will be admitted to hospital for 2-3 days for initiation of the ketogenic diet, during which time the goal will be to transition them from their previous diet to a 1:1 ketogenic diet, and then to a 2:1 ketogenic diet. During hospitalization, urine or plasma ketones and blood glucose will be monitored per the institution's policy for ketogenic diet initiation, and the caregivers will be taught how to do home urine ketone monitoring and home blood glucose testing. The patient may be further transitioned to a 3:1 and then to a 4:1 ketogenic diet after discharge from the hospital. Ketogenic diet management will be performed not only at the University of Minnesota, but also locally by a local ketogenic diet team that works in close communication with the University of Minnesota ketogenic diet team. This teamwork relationship will be established prior to the subject beginning their transition to the ketogenic diet at the University of Minnesota. Communication between the two ketogenic diet teams will occur prior to the subject beginning

their transition to the ketogenic diet at the University of Minnesota, and will recur weekly during the period in which the child is transitioning to the ketogenic diet, as well as whenever questions arise.

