17.0 Study Timetable / Schedule of Events

BL = Baseline, Wk = Week, M = Month, Y = Year

Study Events	Pre-Study	BL	Wk 1	Wk 2	Wk 3	M 1, Wk 4	M 3	M 6	M 9	Y 1 M 12	M 18	Y 2-5 Annual Visits	Y 2-5 Half-Year Time-Point	Every 3 M Throughout this Research Study	Monthly Assessment after the First Year of Study Participation
Determination of leukocyte hexosaminidase activity level for GM ₂ gangliosidosis patients, or β-galactosidase activity level for GM ₁ gangliosidosis patients	X														
Informed Consent		X													
Demographics data collection		X													
Retrospective data collection		X													
Telephone follow-up call: In addition to the timetable shown here, a member of the study staff will contact the parent at least once weekly during the time when the subject is transitioning onto the ketogenic diet, and while the subject is titrating the miglustat dose, and any time the dose is decreased due to adverse events, until symptoms have re-solved. Additionally, while the subject is on a stable (goal) miglustat dose, side effects will be assessed by telephone contact or at clinic visits every 3 months throughout the study period.		X	X	X	X	X	X	X	X	X	X	X	X	X	
Miglustat goal dose = 100 mg 3X daily. Evaluation of dose titration and tolerance of miglustat therapy by tele-phone contact and during clinic visit. After 1 st year, assessments will continue for a minimum of once monthly.			X	X	X	X	X	X	X	X	X	X	X		X
Ketogenic Diet 4:1 Evaluation by ketogenic dietician and neurologist trained in ketogenic diet (a "ketogenic diet team") per institution's clinical program protocol, either at the research site or locally in subject's geographic area. After 1 st year, assessments will continue for a minimum of once monthly.		X	X	X	X	X	X	X	X	X	X	X	X		X
Neuropsychological Testing changes in neuropsychiatric status as assessed by: age-equivalent scores of Bayley Scales of Infant and Toddler Development; and of Vineland Adaptive Behavior Scales		X								X		X			
Neurological evaluation of changes in seizure frequency and severity, and of movement disorders		X								X		X			

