18.0 Data Analysis

18.1 Subject populations for analysis:

- Intention-to-treat Population (ITT): All subjects who initiate any portion of the treatment regimen in association with this study
- Per-protocol Population (PP): Includes all subjects who initiate treatment and are compliant with at least 75% of prescribed drug doses of miglustat, and at least 3:1 ketogenic diet.
- Safety population: All subjects who receive any amount of the combination treatment regimen. Due to the nature of a combination treatment, multiple groups may be identified, should partial adherence be observed.

18.2 Sample size determination. The sample size for the study was determined primarily by feasibility due to the extremely rare nature of the disease. There are two distinct sub-types to be evaluated: infantile and juvenile. Analysis will be based on variability estimates from published natural history studies^{8,11,19} of the infantile form and juvenile form, and correlation between baseline and annual follow-up for up to 4 years.

18.3 Statistical analysis. Descriptive analyses of baseline characteristics and outcomes will include means, standard deviations, medians, and ranges for continuous variables and frequencies for categorical variables. Treatment compliance for each group will also be evaluated. All analyses will be conducted separately for the two disease sub-types – infantile and juvenile – due to the highly heterogeneous patient groups.

The primary analysis for Syner-G treatment regimen will use the intention-to-treat (ITT) population and evaluate overall survival. This will be evaluated based on chronological age at time of death or conclusion of study (whichever occurs first), and compared to available natural history data. Median survival will be compared to previously reported natural history studies of infantile⁹ and juvenile¹¹ forms. Infantile median survival was estimated at 47 months based on data from the National Tay-Sachs and Allied Diseases database for patients born after 2000.⁹ Median survival for the juvenile form was estimated at 14.5 years.¹¹

A secondary endpoint will be the rate of change (i.e., slope) in neurocognitive functioning over the duration of follow-up, compared to available natural history data. This analysis will be conducted separately for each of the two sub-types: infantile and juvenile. The primary

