neurocognitive functioning endpoint for both pediatric groups is age-equivalent scores of the Bayley Scales of Infant and Toddler Development for expressive communication, receptive communication, fine motor skills and gross motor skills. Another primary neurocognitive functioning endpoint for both pediatric groups is age-equivalent scores of the Vineland Adaptive Behavior Scales. Using general estimating equations (GEE) and an exchangeable working correlation structure, variance estimation for confidence intervals and P-values will take into account the possible correlated nature of multiple measurements on the same individual. Supportive analyses will include evaluation using the per-protocol (PP) population.

Safety analyses will be primarily descriptive, reporting the number and percentage of AEs and descriptive summaries. These analyses will use multiple safety populations according to which components of the combination therapy subjects were exposed to. Due to the longitudinal nature of the study and potential for later-emerging effects, the safety profile will be characterized for each sub-type over time. Supportive analyses will include evaluation using the PP population.

Subgroup analyses: analyses will be repeated among GM1 gangliosidosis patients and among GM2 gangliosidosis patients, and among the infantile and juvenile forms of both GM1 and GM2 gangliosidosis.

18.4 Missing data. Despite best efforts to avoid missing data, it is possible that some will occur and will be a potential limitation to the interpretation and generalizability of results. In particular, missing data may arise for non-survival outcomes (e.g. neurocognitive function data) in the event of death. For these instances, it is unclear whether a complete-case analysis (i.e. excluding patients who die) would be unbiased, and therefore would be unsatisfactory. It is also unclear what would be an appropriate magnitude of discount to satisfactorily represent the negative outcome of death. By conducting both the complete-case analysis (unbiased if death is independent of the non-survival outcome) and an analysis with an imputed value for instances of death (intention-to-treat type of analysis), the potential magnitude of treatment effect will be better characterized.

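### Safety populations formed by the components each child was exposed to cannot separate diet effects from combination effects, because newly treated children take the diet alone first

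*Combined protocol and SAP*

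**What the plan says.** Section 18.1 defines the safety population as "All subjects who receive any amount of the combination treatment regimen", so a child who has only started the diet is already in it. It then allows for subdivision: "Due to the nature of a combination treatment, multiple groups may be identified, should partial adherence be observed". Section 18.3 bases the safety analyses on those subdivisions: "These analyses will use multiple safety populations according to which components of the combination therapy subjects were exposed to". The summaries are descriptive counts and percentages. The only time element in 18.3 is a description over time within each disease sub-type (infantile, juvenile), with later-emerging effects in mind.

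Treatment is sequential. Section 11.4 begins with the diet: "The patients will be admitted to hospital for 2-3 days for initiation of the ketogenic diet". Further steps up to a 4:1 ratio may follow after discharge, with no stated duration. Section 10.11 then requires "showing stability on the ketogenic diet for 2 weeks before starting miglustat therapy". Section 10.12 titrates miglustat over about 8 weeks, and 10.13 provides for reductions, holds, stops and restarts.

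The 17.0 table has a row reading "Miglustat goal dose = 100 mg 3X daily. Evaluation of dose titration and tolerance of miglustat therapy by tele-phone contact and during clinic visit", marked from Week 1. The diet row is marked from baseline.

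**The concern.** A child's exposure changes several times: diet alone, diet with miglustat being titrated, diet with miglustat at a steady dose, and possibly diet with miglustat held. A label fixed per child cannot follow those changes. Once a child has taken miglustat, the child has been exposed to both components, and the plan gives no rule that keeps events from before the first miglustat dose out of that group's table.

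This matters because 18.3 sets out to describe safety by component, and the expected effects differ by component: mainly constipation, lethargy and early seizure increase for the diet, and mainly diarrhoea and weight loss for miglustat. If diet-initiation events sit in the both-components table, a reader cannot tell what starting the diet does from what adding miglustat does. The diet-only table would hold only children who had not gone on to miglustat, who are a selected group.

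**Working it through.** The documents give no adverse event rate, power or precision target for safety, so there is no planned figure to reproduce. The check sets the rules side by side and then sizes the gap.

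**1. Unit of grouping.** Sections 18.1 and 18.3 both classify subjects. The trigger for separate groups in 18.1 is partial adherence. The diet-alone phase of a fully adherent child is planned treatment, so it triggers no group.

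**2. Length of the diet-alone phase (newly treated child).** Inputs: 2-3 days of initiation (11.4), 14 stable days (10.11), and a transition T that the documents do not give.

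Days on diet alone = (2 to 3) + T + 14.

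- T = 0: 16-17 days. 16/365 = 4.4% and 17/365 = 4.7% of year 1; 16/1826 to 17/1826 = about 0.9% of five years.
- T = 56 days (assumed upper value): 72-73 days, about 20% of year 1 and about 4% of five years.

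The share of follow-up is small. But 11.2, 11.4 and 20.3 place constipation, lethargy and the transient seizure increase at initiation or transition.

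**3. Where diet-alone events are counted.** Suppose 30 newly treated children, a fraction q of whom never start miglustat, with equal event risk in those who do and do not start (both assumed). The share of diet-alone events falling in the both-components population is 1 - q.

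- q = 0: diet-only group 0 children, share 100%.
- q = 10%: diet-only group 3, share 90%.
- q = 20%: diet-only group 6, share 80%.

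**4. Effect on a reported percentage (illustration).** Let pL be the probability that a child has the event with onset on diet alone, and pC the probability of onset on the combination. Take them as independent, with all 30 children going on to miglustat. The subject-level figure is pL + (1 - pL) x pC. The onset-based combination figure is pC.

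- pL = 30%, pC = 10%: 0.30 + 0.70 x 0.10 = 37% (11.1 of 30). By onset: 10% (3 of 30) on the combination and 30% (9 of 30) on diet alone.
- Over pL 10-50% and pC 10-30%: the subject-level figure is 19-65%, against 10-30% by onset. The share of affected children whose first event came on diet alone, pL divided by the subject-level figure, is 27% (0.10/0.37) to 91% (0.50/0.55).

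**5. Other provisions that might separate the events.**

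- The description over time in 18.3 is by disease sub-type, not by component or treatment phase.
- The aggregate reports in 19.1 give relationship to study procedures, without splitting diet from drug.
- The medical reviewer's causality rating in 19.5 covers serious events and is not by component.
- Sections 19.3 and 20.0 list risks separately for each component, but that is not a rule for assigning events.

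**6. Visit labels.** The 17.0 notes place children already on the regimen at the time-point matching their time on Syner-G, but do not say whether that clock starts with the diet or with miglustat. If it starts with the diet, the earliest miglustat start for a newly treated child falls in the third week (day 16-17), and the Week 1 and Week 2 miglustat entries precede it. If it starts with miglustat, they fit. Phase therefore cannot be read from visit labels.

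**The case against.** Starting the diet is the first step of the regimen. For the question of what happens to a child who begins Syner-G, counting diet-initiation events is correct, and a population defined by any amount of the regimen does that. This stands, and it is why the subject-level populations should be kept. It is also true that 12.0 lists survival and neurodevelopment as objectives, not safety, and that the safety analysis is descriptive with no planned test between groups. That limits the consequence. It does not remove it, because 18.3 announces a component-based description that its rule cannot deliver.

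Four stronger readings are tempting and are not supported:

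- A reader might infer that the plan treats diet-phase events as combination toxicity. It does not say so. It is silent on onset, and being counted in a population is not attribution.
- A reader might infer that nearly all 30 children are affected and that a miglustat-only group would be almost empty. Section 13.6 admits children already on miglustat and/or the diet, 17.0 has a rule for those already on the regimen, and 24.3 describes patients already treated with both. The newly treated share is unknown.
- A reader might measure the diet-alone phase against the first three months: an assumed 1-4 week transition plus 2 stable weeks gives 3-6 weeks, or 3/13 = 23% to 6/13 = 46% of 13 weeks. That rests on an assumed transition and a chosen window, and a share of time is not a share of events.
- A reader might see a flat contradiction between 10.11 and Week 1 in 17.0. A child already stable on the diet at entry could be taking miglustat by then. What is established is that time zero is undefined.

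**Conclusion.** The concern holds for newly treated children who go on to miglustat. For them, every event that starts in the diet-alone phase is counted in the both-components population, and nothing in the plan separates it by onset or component. The documents fix that phase at 16-17 days at the least; its full length depends on an unstated transition. The effect on reported percentages cannot be computed from the documents. The shift from 10% to 37% is an illustration on assumed rates, with all 30 children newly treated and starting miglustat, and it shrinks as more children enter already on treatment. The conclusion relies on reading exposure in 18.3 as any exposure during the study; the text gives no other rule. This is a worthwhile, inexpensive repair to a descriptive analysis. It does not affect the survival or neurodevelopmental analyses.

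**What to change.** Keep the subject-level safety populations in 18.1 for whole-regimen safety. Add to 18.3 a table of adverse events by exposure at onset:

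- diet only, before the first miglustat dose;
- diet plus miglustat;
- miglustat held or stopped while on the diet;
- miglustat without the diet.

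Give the number of children and the person-time in each category, since the phases differ greatly in length. Derive the categories from start, stop and hold dates for each component. For children already on a component at enrollment, assign by actual exposure at onset.

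Leave events that start during a hold or after a stop as their own category. A fixed carry-over from the stated plasma half-lives (five times 6-7 h or about 10 h, so 30-50 h, about 2 days) should not be used to reassign them: 10.13 follows platelets for 2 weeks and neuropathy at 1-month intervals, so those effects are expected to outlast such a window.

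Define time zero in 17.0 and reconcile its Week 1 miglustat entries with 10.11.

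Cost: SAP wording, one derived variable and one table. No new visits or samples should be needed, because 17.0 already requires contact at least weekly during diet transition and titration. The documents do not list case report form fields for component dates, so these must be added if absent, including dates held by local diet teams. Cells will be sparse, with 15 children planned per sub-type, and the table should be read as description only.

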13.0 Study Design

13.1 Overview of study design. Both retrospective and prospective data will be collected during this study. This is a single-arm treatment protocol, with intention-to-treat per-protocol design. The primary analysis for Syner-G treatment regimen will use the intention-to-treat (ITT) population and evaluate overall survival. This will be evaluated based on chronological age at time of death or conclusion of study (whichever occurs first), and compared to available natural history data. This will be conducted separately for each of the two sub-types: infantile and juvenile. The neurocognitive functioning endpoint for both groups is the cognition domain of the Bayley Scales of Infant and Toddler Development for expressive communication, receptive communication, fine motor skills, gross motor skills; and the Vineland Adaptive Behavior Scales. Each of the other 4 domains will be evaluated as secondary endpoints. Using general estimating equations (GEE) and an exchangeable working correlation structure, variance estimation for confidence intervals and P-values will take into account the possible correlated nature of multiple measurements on the same individual. Supportive analyses will include evaluation using the per-protocol (PP) population.

Subgroup analyses: analyses will be repeated among GM1 gangliosidosis patients and among GM2 gangliosidosis patients, and among the infantile and juvenile forms of both GM1 and GM2 gangliosidosis.

Yearly evaluations, whenever possible, will also explore changes in seizure frequency and severity, and in movement disorders, evaluated by neurologist and parent-report.

Some subjects do not have insurance coverage for certain evaluations. Sometimes the insurance coverage changes and clinical care that was covered in the past is no longer covered. The investigators will continue to see these patients annually, whenever possible, and will provide the scheduled clinical-care visits according to what is allowed within the restrictions of the subject's health care insurance. When any given subject is unable to make their annual visit to the University of Minnesota due to illness or weakness, this will not cause them to be withdrawn from the research study. The reason for foregoing the evaluation will be documented in the subject's file, and the investigators will continue to follow them through telephone contacts with family members and health care providers.

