Measurement of subject weight, height, occipital-frontal circumference, comprehensive metabolic panel (including serum creatinine, estimated GFR, and liver function tests), CBC with plate-lets and differential, lipid panel, neurologic exam to assess for peripheral neuropathy, and urine pregnancy test in all post-pubertal females. It is accept-able for this interval safety monitoring to not occur at the primary study site as long as the neurologic exam is performed by an experienced practitioner.		X					X	X	X	X	X	X	X		

Whenever possible, the scheduled assessments/exams will be conducted on all subjects for the duration of the study. However, due to disease progression or concurrent illness, some patients after enrollment may not be able to fulfill the annual visit requirement. If this occurs, a failure to appear for any given annual visit will not make any subject ineligible to continue as a research participant. For research purposes, the rarity of the gangliosidoses dictates that as much data as possible be collected on any given subject.

When any newly-enrolled subject is already using the Syner-G regimen at time of enrollment, for clinical management, the Schedule of Events for that subject will begin with the scheduled time-point that corresponds to the number of weeks or months that subject has been using Syner-G.

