Missing data may also arise from “lost to follow-up.” The last-observation-carried-forward imputation will be used to satisfy this type of missing data. Sensitivity analyses to evaluate the extent to which results are dependent on the approach to missing data will be conducted, wherein multiple imputations will also be considered.

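### LOCF for children lost to follow-up flattens the secondary neurocognitive slope while decline continues; the planned GEE on observed scores should be the main analysis, with rules set for deaths and missed testing

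*Combined protocol and SAP*

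**What the plan says.** Section 18.3 makes the secondary endpoint "the rate of change (i.e., slope) in neurocognitive functioning over the duration of follow-up, compared to available natural history data". It is estimated by GEE with an exchangeable working correlation, separately for the infantile and juvenile sub-types. Section 17.0 schedules Bayley and Vineland testing at baseline, Year 1 and the annual visits of Years 2-5; section 18.2 speaks of "correlation between baseline and annual follow-up for up to 4 years".

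Section 18.4, repeated in 22.1, deals with two sources of missing scores:

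- **Loss to follow-up.** "The last-observation-carried-forward imputation will be used to satisfy this type of missing data". Sensitivity analyses on the approach to missing data are promised, "wherein multiple imputations will also be considered", with no further content.
- **Death.** The plan says "it is unclear whether a complete-case analysis (i.e. excluding patients who die) would be unbiased, and therefore would be unsatisfactory" and concedes that it does not know how heavily death should count. It will run that analysis and a second one with an imputed value. Neither is named as main, and no value is given.

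A third source is foreseen but has no analysis rule. Section 13.1 expects children "unable to make their annual visit to the University of Minnesota due to illness or weakness", and 17.0 says that "due to disease progression or concurrent illness, some patients after enrollment may not be able to fulfill the annual visit requirement". These children stay in the study and are followed by telephone, so they are neither dead nor lost.

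**The concern.** Section 1.1.3 describes untreated children as declining in a foreseeable way until death. Carrying a score forward asserts the opposite, namely no change after the last test. In a single-arm study judged against external natural history, a slope nearer zero would be taken as a treatment effect, and LOCF can produce one without any.

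The other two gaps concern the same slope. The survivors-only analysis discards scores actually observed before death. The imputed-death analysis cannot be run as written, because its value is missing. Whether an enrolled but untested child is carried forward is left to whoever does the analysis.

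**Working it through.** The plan gives no power, loss rate or slope figure for this endpoint, so there is nothing of its own to reproduce.

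**1. One child, exact.** Let the true decline be linear, with annual visits t = 0..T and the last test at visit d. After LOCF the share of the slope kept is Σ(t − t̄)·min(t, d) / Σ(t − t̄)². For T = 5 the denominator is 17.5. With d = 2 the numerator is −1.5 − 1 + 1 + 3 + 5 = 6.5, and 6.5/17.5 = 0.371.

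| Last test | Baseline | Y1 | Y2 | Y3 | Y4 |
|---|---|---|---|---|---|
| Visits 0-5 (section 17.0) | 0% | 14% | 37% | 63% | 86% |
| Visits 0-4 (section 18.2) | 0% | 20% | 50% | 80% | – |

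This applies to children not tested again. One missed visit filled by LOCF, with later testing, leaves 109, 103, 97 or 91% of the slope (missed at Year 1, 2, 3 or 4 of visits 0-5).

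**2. Pooled slope, exact.** With a share p lost and last tests spread evenly, the share kept is 1 − p(1 − m), where m is the row mean: 0.40 for visits 0-5 and 0.375 for 0-4.

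| Assumed loss | 10% | 20% | 30% | 40% |
|---|---|---|---|---|
| Visits 0-5 | 94% | 88% | 82% | 76% |
| Visits 0-4 | 94% | 88% | 81% | 75% |

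If nobody is lost straight after baseline, m = 0.50 and the shares are 95, 90, 85 and 80%.

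**3. Against sampling error.** Assume a slope of −3 months per year, between-child slope SD 2, residual SD 1 and 15 children per sub-type (3 × 5, section 13.3). Then SE = √((2² + 1/17.5)/15) = 0.52. The bias for visits 0-5 runs from 3 × 0.06 = 0.18 at 10% loss to 3 × 0.24 = 0.72 at 40%, or 0.3 to 1.4 SE.

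**4. Simulation without a floor.** Same inputs, starting level 24 months (SD 4), loss unrelated to slope. With 2, 3, 5 or 6 of 15 lost, GEE after LOCF gives −2.76, −2.65, −2.39 or −2.30, with 95% interval coverage of 91, 88, 76 or 70%. GEE on observed scores gives −3.01, −3.01, −2.98 or −3.02, with coverage of 90-93%.

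**5. Simulation with a floor at 0.** Age-equivalent scores cannot be negative. The starting levels are assumed.

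| Start (months) | True slope | Lost of 15 | Coverage, LOCF | Coverage, observed-score GEE |
|---|---|---|---|---|
| 24 | −2.79 | 6 | 68% | 88% |
| 12 | −1.81 | 6 | 80% | 87% |
| 6 (SD 2) | −0.90 | 3 | 93% | 82% |
| 6 (SD 2) | −0.90 | 6 | 89% | 78% |

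At 3 lost the methods are about level for starts of 24 and 12. At a start of 6, LOCF is still too flat (−0.84 and −0.77), while observed-score GEE is too steep (−0.94 and −0.97). A 2,000-run repeat with these inputs kept the ordering at the low start but narrowed the gap (94% v 89%, 88% v 81%).

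**6. Deaths.** Inputs as in step 4, death unrelated to slope, no LOCF, 25% or 50% dead. Survivors-only and half of the last value both stay near −3. Scoring death as 0 gives −3.45 or −3.87, a shift of 0.45/0.52 = 0.9 SE or 0.87/0.52 = 1.7 SE.

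**The case against.** The strongest reply is that the size is unknown and probably modest.

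- **Loss may be low.** Children who miss visits stay enrolled, so few may count as lost. At 2 of 15 lost, LOCF coverage (91%) is no worse than that of observed-score GEE (90-93%). This stands: 40% is the end of a range, not an expectation.
- **The floor matters.** Near it, LOCF intervals can cover better. This stands as well, though LOCF still leans towards benefit there and observed-score GEE leans against it.
- **Sensitivity analyses are already planned.** True, but they are unspecified, and LOCF remains the stated method.
- **GEE accepts unequal numbers of visits,** so untested visits can simply drop out. That is the remedy proposed here; the plan does not say it.

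A reader might infer that the unstated death value decides the result. The figures do not support that: mild values barely move the slope, and of those tried only scoring death as 0 does. A reader might also infer that the survivors-only analysis is itself flattened. With death unrelated to slope and no LOCF it stays near −3, in line with the plan's own statement that it is then unbiased.

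**Conclusion.** The point holds as a correctable choice of analysis for the secondary endpoint. For a child still declining and not tested again, the flattening is arithmetic and needs no assumption beyond linear decline. The pooled figures, about 6% at 10% loss and about 25% at 40%, also rest on assumed loss rates and evenly spread last tests. The standard-error and coverage figures further assume slopes, SDs and starting levels that the documents do not give.

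It would be tempting to conclude that the trial's slope comparison must favour Syner-G. The documents do not support that. LOCF adds little near the floor and works against Syner-G while skills are being gained, and section 24.3 reports improvement in some domains. With no natural-history Bayley or Vineland slope given either, the net direction is open. The primary survival analysis is not touched.

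**What to change.** In 18.4 and 22.1:

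- Make the planned GEE on all observed scores, up to death, loss or the last completed test, the main slope analysis in each sub-type. Include the scores of children who later die, and carry nothing forward. Keep LOCF only as a sensitivity analysis.
- Say that enrolled children who miss testing (13.1, 17.0) are handled the same way.
- Label the survivors-only analysis as supportive, and fix in advance the value used in the imputed-death analysis.
- Report the numbers lost, untested and at the floor per sub-type.

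A mixed model with random slopes and a delta-adjusted multiple imputation are optional sensitivity analyses; the defect does not require them.

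The cost is wording and light programming, with no new data. The slope may look less favourable. Precision falls: without a floor, at 6 of 15 lost, the empirical SD is 0.60 for observed-score GEE against 0.46 for LOCF. Decline is modestly overstated when many children reach the floor. Bias remains if loss or death depends on the rate of decline. With loss weighted 2.2 per SD of slope and 3 or 6 of 15 lost, observed-score GEE gives −2.74 or −2.56 against a true −3; LOCF gives −2.49 or −2.08.
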